#### **6.2.1.11. Counting Rules for Occurrences of Solicited Events starting during the solicitation period**

When the occurrences of solicited events are summarized, each event recorded as having occurred during a specific period will be counted as only 1 occurrence regardless of the number of days on which it occurs.

### 6.2.1.12. AESIs

GSK MedDRA queries will be used to identify AESI:

- pIMD: refer to Table 9 from the protocol
- Severe hypersensitivity (including anaphylaxis): Grade 3 unsolicited AEs under MedDRA SMQ hypersensitivity, narrow search (includes anaphylaxis), with an onset within 24 hours after dosing

Myocarditis/pericarditis. In addition to identification based on the medical and scientific judgement of the investigator, the following non-exhaustive list of PTs will be used: autoimmune myocarditis; eosinophilic myocarditis; giant cell myocarditis; hypersensitivity myocarditis; immune-mediated myocarditis; myocarditis; autoimmune pericarditis, pericarditis; pericarditis adhesive; pericarditis constrictive; pleuroperticarditis.

These pIMD, myocarditis and pericarditis queries may be revised based on MedDRA dictionary version.

AESI summaries will include AEs identified by either the investigator or the MedDRA queries.

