#### **8.4.4. AESIs**

The study will capture the following specific AESIs:

- pIMDs
- Any laboratory-confirmed moderate to severe case of COVID-19
- Myocarditis and pericarditis
- Anaphylaxis or severe hypersensitivity within 24 hours after study intervention administration

All suspected cases of COVID-19, myocarditis, and pericarditis in study participants will be diagnosed and clinically evaluated, which may require unscheduled study site visits and additional testing based on the investigator's judgment.

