**Table 16 Intensity scales for solicited events**

Event	Intensity grade	Parameter
Pain at administration site	0	None
	1	Mild: Any pain neither interfering with nor preventing normal everyday activities
	2	Moderate: Painful when limb is moved and interferes with everyday activities
	3	Severe: Significant pain at rest. Prevents normal everyday activities
Redness at administration site	0	<2.5 cm
	1	2.5 – 5 cm
	2	5.1 – 10 cm
	3	>10 cm
Swelling at administration site	0	<2.5 cm
	1	2.5 – 5 cm
	2	5.1 – 10 cm
	3	>10 cm
Lymphadenopathy*	0	None
	1	Mild: No interference with activity
	2	Moderate: Some interference with daily activity or requires repeated use of non-narcotic pain reliever
	3	Severe: Prevents daily activity or requires use of narcotic pain reliever
Temperature**	0	<38.0°C or <100.4°F
	1	38.0 – 38.4°C or 100.4 – 101.1°F
	2	38.5 – 38.9°C or 101.2 – 102.0°F
	3	>38.9°C or >102.0°F
Headache	0	Normal
	1	Mild: Headache that is easily tolerated
	2	Moderate: Headache that interferes with normal activity
	3	Severe: Headache that prevents normal activity
Fatigue	0	Normal
	1	Mild: Fatigue that is easily tolerated
	2	Moderate: Fatigue that interferes with normal activity
	3	Severe: Fatigue that prevents normal activity
Myalgia	0	Normal
	1	Mild: No interference with daily activity
	2	Moderate: Interferes with daily activity
	3	Severe: Prevents daily activity
Arthralgia	0	Normal
	1	Mild: No interference with daily activity
	2	Moderate: Interferes with daily activity
	3	Severe: Prevents daily activity

Event	Intensity grade	Parameter
Chills	0	None
	1	Mild sensation of cold; shivering; chattering of teeth
	2	Moderate tremor of the entire body; narcotics indicated
	3	Severe or prolonged, not responsive to narcotics

\* Defined as localized axillary, cervical or supraclavicular swelling or tenderness ipsilateral to the vaccination arm.

\*\* Refer to Section 10.3.3 for the preferred location for temperature measurement.

The investigator will make an assessment of intensity for each AE/AESI/SAE reported during the study and assign it to one of the following categories:

- Mild:  
A type of AE that is usually transient and may require only minimal treatment or therapeutic intervention. The event does not generally interfere with usual activities of daily living.
- Moderate:  

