A type of AE that is usually alleviated with additional specific therapeutic intervention. The event interferes with usual activities of daily living, causing discomfort but poses no significant or permanent risk of harm to the research participant.
- Severe:  
A type of AE that interrupts usual activities of daily living, or significantly affects clinical status, or may require intensive therapeutic intervention.

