#### 4.8. Changes to Protocol Defined Analyses

There were no changes or deviations to the originally planned statistical analysis specified in the protocol amendment 1 (Dated: 26 September 2023).

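### The SAP's hypersensitivity query filters anaphylaxis on Grade 3, but the AESI definition states no grade for anaphylaxis, so the query cannot return a lower-grade or ungraded case

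*SAP*

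**What the plan says.** Protocol sections 8.4 and 8.4.4 list four AESIs. One is "Anaphylaxis or severe hypersensitivity within 24 hours after study intervention administration". Section 2.3.1 uses the same formula when it describes how the hypersensitivity risk is mitigated, and SAP 4.2.1.3 repeats it when it defines the AESIs to be summarised. None of these places states a grade for anaphylaxis.

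SAP 6.2.1.12 turns the definition into a search rule. The label of the rule begins "Severe hypersensitivity (including anaphylaxis", and the rule selects "Grade 3 unsolicited AEs under MedDRA SMQ hypersensitivity, narrow search (includes anaphylaxis), with an onset within 24 hours after dosing". The same section then says: "AESI summaries will include AEs identified by either the investigator or the MedDRA queries".

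On intensity, protocol 10.3.6.3 says: "The investigator will make an assessment of intensity for each AE/AESI/SAE reported during the study and assign it to one of the following categories". The categories are mild, moderate and severe. SAP 6.2.2.3 says that a missing severity for an unsolicited AE is not replaced and is displayed as unknown.

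**The concern.** The definition has two limbs: anaphylaxis, or hypersensitivity that is severe. The query has one limb: severe hypersensitivity, with anaphylaxis inside it. Moving anaphylaxis under the severity condition narrows what the query can find.

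This deserves a line in a review because AESI occurrence is a primary safety endpoint in both Part A and Part B, and hypersensitivity including anaphylaxis is the first important potential risk named in protocol 2.3.1. The summaries combine investigator-identified and query-identified events, so the query's practical contribution is to add events that the investigator did not identify. For anaphylaxis below Grade 3 it adds nothing. The myocarditis and pericarditis term list in the same SAP section carries no grade filter, so a grade restriction is not a general feature of these searches.

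**Working it through.** The plan gives no figure to reproduce. The check sets the definition beside the query and runs each type of event through both. All events below have onset within 24 hours of dosing. I take Grade 3 to mean severe, as the headings of SAP Tables 6 and 7 do for solicited events; the documents do not state the mapping for unsolicited AEs.

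| Event | Meets the AESI definition (protocol 8.4.4, SAP 4.2.1.3) | Returned by the query (SAP 6.2.1.12) | In AESI summary if the investigator has not identified it |
|---|---|---|---|
| Anaphylaxis, severe | Yes | Yes | Yes |
| Anaphylaxis, mild or moderate | Yes, no grade is stated | No | No |
| Anaphylaxis, severity missing | Yes, no grade is stated | No | No |
| Other hypersensitivity, severe | Yes | Yes | Yes |
| Other hypersensitivity, mild or moderate | No | No | No |

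Definition and query agree in rows 1, 4 and 5 and disagree in rows 2 and 3.

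Can rows 2 and 3 occur under the plan's own rules?

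- Row 2: intensity is the investigator's judgement, made separately for each event. The moderate category opens with "A type of AE that is usually alleviated with additional specific therapeutic intervention", which does not rule out a treated allergic reaction. Nothing in either document makes anaphylaxis Grade 3 by definition.
- Row 3: because missing severity is not replaced, an ungraded event cannot satisfy a Grade 3 condition.

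What happens to such an event:

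1. If the investigator identifies it as an AESI, it enters the AESI summary, because the two routes are combined.
2. If not, it is absent from the AESI summary. With onset within 24 hours it falls inside the Day 1 to Day 28 window, so it still appears in the unsolicited AE tabulation by preferred term and system organ class, and in the listing (SAP 4.2.1.2).

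Size of one case: planned arms are 415/5 = 83 in Part A and 249/3 = 83 in Part B, so one event is 1/83 = 0.012, or 1.2% of an arm. This is the weight of a single event, not an estimate of how often it would be missed. The documents give no rate from which to derive that.

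**The case against.** The strongest reply is that the query can only add events and never remove one. An anaphylaxis identified by the investigator is summarised whatever its grade. That is correct. A reader might infer that lower-grade anaphylaxis is dropped from the AESI tables, and the documents do not support that: only the query route is closed to it.

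A second reply is that the protocol does not say that anaphylaxis of any grade is an AESI. That is also correct: it is silent on grade, and the table above relies on that silence. Exclusion criterion 9 lists anaphylaxis among the examples of hypersensitivity or severe allergic reactions, and the SAP label can be read in the same spirit. Even so, the AESI definition keeps the two limbs apart, and the SAP repeats it in that form.

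Third, a rating below severe would be unusual. The full description of moderate adds that the event carries no important or lasting risk of harm, while severe covers events that materially change clinical status or can call for intensive treatment. Detection at the site should also be good: at least 30 minutes of observation, an instruction to contact the site at once for a possible reaction within a day, and AESI reporting within 24 hours. These points make a missed case unlikely. They do not make the query match the definition.

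Finally, a reader might treat SAP 4.8, which says "There were no changes or deviations to the originally planned statistical analysis specified in the protocol amendment 1", as a false statement. That goes too far. SAP 4.2.1.3 keeps the protocol definition, and a narrow supplementary search is not clearly a changed analysis. The fair observation is only that nothing tells the reader that the query is narrower than the definition.

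**Conclusion.** The point holds in a limited form. The query in SAP 6.2.1.12 does not implement the AESI definition in protocol 8.4 and 8.4.4 and SAP 4.2.1.3: it cannot return an anaphylaxis AE rated below Grade 3 or left ungraded. The AESI count would be affected only if such an event occurred and the investigator did not identify it, and even then it would remain visible elsewhere in the safety output.

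The expected effect is very small. No decision rule depends on this count, because the study is descriptive. The conclusion rests on two assumptions: that silence on grade means no grade condition on anaphylaxis, and that Grade 3 for unsolicited AEs corresponds to the protocol's severe category. This is a low-priority correction, worth making because it is nearly free and concerns a primary safety endpoint.

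**What to change.** In SAP 6.2.1.12, replace the single hypersensitivity rule with two:

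- (i) anaphylaxis terms (anaphylactic reaction SMQ, narrow search), no grade filter, onset within 24 hours of dosing;
- (ii) the other terms of the narrow hypersensitivity SMQ, Grade 3, onset within 24 hours of dosing.

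Rows 2 and 3 of the table then agree with the definition, and the other rows do not change. If the narrower search is intended, a sentence in SAP 6.2.1.12 or 4.8 saying so would suffice. The cost is one additional query and an occasional extra hit that needs medical review. No data collection changes.

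Separately, and only as a clerical correction, the pIMD entry in the same section refers to protocol Table 9. In Protocol Amendment 1 that table lists biological samples, and the pIMD list is Table 13. The reference can be corrected in the same edit. It has no bearing on the point above.

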## 6.2.2. Handling of Partial Dates

### 6.2.2.1. Dates

When partially completed dates (i.e., dates missing a day and/or month) are used in calculations, the following standard rules will be applied:

- A missing day will be replaced by 15
- A missing day and month will be replaced by June 30th.
- For stop date, the maximum between the start and imputed stop date by above rule will be used instead.

The following exceptions apply:

- Adverse events start dates on the same day as the vaccination but with missing time:
  - Onset day will be day 1.
- Adverse events start dates with missing day:
  - If the event starts in the same month as the study dose administration then the imputed start date will match the study dose given during that month.
- Adverse events start dates with missing day and month:
  - If the event starts in the same year as the study doses the imputed start date will match the study dose given during that year.

- Adverse events stop dates with missing day: the last day of the month or the last contact date will be used, which ever come first.
- Adverse events stop dates with missing day and month: the last day of December or the last contact date will be used, which ever come first.
- Adverse events stop dates with missing day, month, and year: the last contact date will be used.

All other cases of incomplete AE or concomitant medication/vaccination start date will follow the standard rules above.

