## 3. ANALYSIS SETS

**Table 1 Analysis set definition and analyses evaluated**

Analysis Set	Definition / Criteria	Analyses Evaluated
Enrolled	
 
All participants who entered the study (who were randomized or received study intervention or underwent a post-screening procedure)
 
 
NOTE: screening failures (who never passed screening even if rescreened) and participants screened but never enrolled into the study (Met eligibility but not needed) are excluded from the Enrolled Analysis set as they did not enter the study.
	
 
Study Population
 

Exposed Set (ES)	
 
Participants who received study intervention
 
Participants will be analysed according to the study intervention administered.
 
	
 
Safety, immunogenicity if applicable, demography
 

eDiary Set	
 
All participants in the Safety analysis set for whom eDiary data are available (complete or partial).
 
	
 
Solicited AEs
 

Per-Protocol Set (PPS)	
 
All participants from the ES who were eligible, complied with vaccination as per protocol (e.g., vaccine not expired, with appropriate temperature storage), and had a pre-dose and Day 29 anti-neutralizing titer against either the CCI [REDACTED] CCI [REDACTED] strains.
 
 
Immunogenicity data at a post-vaccination visit will be censored in case of noncompliance for the blood sample visit. Likewise, immunogenicity data after the following intercurrent event will be censored: COVID-19, immunosuppressive or immunodeficient conditions, COVID-19 vaccination and prohibited medication/vaccination after study intervention.
	
 
Immunogenicity, demography
 

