#### 6.1.4.      Prior and Concomitant Medications

Concomitant medications are defined as any medications and vaccines (other than study intervention) taken after the study intervention administration. Any medication or vaccine (other than study intervention) started prior to the study intervention administration and continued after the study intervention administration will be considered a concomitant medication.

Concomitant medications/vaccinations will be coded using both the GSK Drug and WHO Drug dictionaries and will be listed and summarized descriptively (any medication, any antipyretic, and any antipyretic taken prophylactically, respectively) by study group using the ES.

The antipyretic classification is derived from the following ATC code

ATC Code
A03D, A03DA, A03DB, A03DC, A03EA
M01, M01A, M01AA, M01AC, M01AE, M01AG, M01AB, M01AH, M01AX, M03B, M03BA, M03BB, M03BB, M03BC, M03BX
N02BG, N02AC, N02AG, N02AX, N02B, N02BA, N02BB, N02BE
R05, R05D, R05X

The percentage of participants using concomitant medication (any medication, any antipyretic and any antipyretic taken prophylactically, respectively) during the 28-day follow up period (i.e., Day 1-Day 28 post-dose) will be summarized by group.

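### SAP 6.2.2.1 imputes partial concomitant medication and vaccination dates without reference to the dose date, so some short post-dose treatments are classed as pre-dose

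*SAP*

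**What the plan says.** SAP 6.2.2.1 sets two general rules for partial dates. For the day, "A missing day will be replaced by 15"; a missing day and month together become June 30. For stops, "For stop date, the maximum between the start and imputed stop date by above rule will be used instead", so an imputed stop is compared with the start and never with the dose.

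Exceptions follow, all for adverse events. An event start known only to the dosing month is anchored to dosing: "the imputed start date will match the study dose given during that month". A start known only to the dosing year is handled in the same way. Partial event stops go to the end of the month or year, or to last contact if that is earlier. Medications and vaccines get none of this: "All other cases of incomplete AE or concomitant medication/vaccination start date will follow the standard rules above".

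These dates feed three places:

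- SAP 6.1.4, classification: "Concomitant medications are defined as any medications and vaccines (other than study intervention) taken after the study intervention administration". A carry-over clause adds that a product "started prior to the study intervention administration and continued after the study intervention administration will be considered a concomitant medication".
- SAP 6.1.4, by-group summary: the percentage of participants using any medication, any antipyretic or a prophylactic antipyretic over Days 1-28.
- SAP Table 1: titers are censored after certain intercurrent events, among them "COVID-19 vaccination and prohibited medication/vaccination after study intervention".

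Protocol 6.9 has sites record medications and vaccinations from 6 months before eligibility assessment to study end, plus all prior COVID-19 vaccines. Drug name and administration dates are the minimum record.

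**The concern.** The medication dataset holds treatments from both sides of the dose, so the date decides which side a record falls on. SAP 6.2.1.7 applies its onset-day definition to concomitant medications and vaccinations as well as to adverse events, so imputed dates enter that calculation. The SAP guards against an imputed date falling before the dose for adverse events but not for treatments.

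What is at stake is mainly the completeness of a descriptive output. Antipyretic use in the days after vaccination is useful background for reading the solicited event rates, and the first week is where a mid-month imputation most often crosses the dose date. A secondary question is whether an imputed vaccine or drug date could also mislead the censoring of titers in the Per-Protocol Set.

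**Working it through.** The plan gives no figure to reproduce, so the rules were applied to calendar dates.

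**Worked cases, dose on 20 October 2023**

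| True treatment | Recorded as | Imputed | Result |
|---|---|---|---|
| Drug started 22 Oct, short course | start Oct, stop Oct | 15 Oct to 15 Oct | classed as pre-dose, missed |
| Drug 22 to 24 Oct | start Oct, stop 24 Oct | 15 Oct to 24 Oct | kept by the carry-over clause |
| Drug started 2 Nov | start Nov, stop Nov | 15 Nov to 15 Nov | correctly post-dose |

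A vaccine has a single date, so a vaccine given on 22 October and recorded as October behaves like the first row.

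**When only the year is known.** A 2023 record becomes 30 June 2023. Part B was added by the protocol amendment of 26 September 2023, so every such record in Part B is dated before the dose.

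**Share of day-missing starts imputed before the dose.** Assumptions: dose dates uniform over the 365 days of 2023; true start uniform over the first w days, with Day 1 the dose day; month and year known. A post-dose start is imputed before the dose only if the dose is on the 16th or later (185 of 365 dates, 50.7%) and the start is in the dosing month.

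- w = 7: 185 × 7 = 1,295 dose-start pairs. Those crossing into the next month number 12 × (1+2+…+6) = 252. (1,295 − 252) / (365 × 7) = 1,043 / 2,555 = **40.8%**.
- w = 14: 185 × 14 − 12 × (1+2+…+13) = 2,590 − 1,092 = 1,498. 1,498 / 5,110 = **29.3%**.
- w = 28: a month with n dose days after the 15th gives n(n+1)/2 pairs. 7 × 136 + 4 × 120 + 91 = 1,523. 1,523 / 10,220 = **14.9%**. A further 12.3% are imputed beyond Day 28; they stay concomitant but would fall outside a Day 1-28 summary based on start date.

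**Reverse error.** A start 1-7 days before dosing is imputed on or after the dose if the dose is on or before the 15th and the start is in the same month. Each month has (1+2+…+7) + 7 × 7 = 77 pairs. 12 × 77 / 2,555 = 924 / 2,555 = **36.2%**. For starts 1-28 days before dosing: 12 × (1+2+…+14) / 10,220 = 1,260 / 10,220 = 12.3%.

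**Effect of copying the adverse event start rule.** The share of true post-dose starts imputed before the dose falls to 0% in all three windows. But day-missing starts 1-7 days before dosing then move to the dose date whenever they share its month: (2,555 − 12 × 28) / 2,555 = 2,219 / 2,555 = 86.8%, unless the record shows that they were pre-dose.

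**Scale.** The rate of partial dates is not in the documents. As an illustration, suppose all 83 participants in a group took one antipyretic on Days 1-7. If 1% of starts lacked the day, at most 83 × 0.01 × 0.408 = 0.3 records would be imputed before the dose; at 5%, at most 1.7. Fewer would be lost, because the stop date must also be partial.

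**The case against.** Four points on the other side have force.

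- **Few records are lost.** The carry-over clause in SAP 6.1.4 keeps any product with a known post-dose stop or still ongoing. The 40.8% therefore describes imputed start dates; a reader who took it as the share of treatments missed would be wrong. Protocol 6.9 makes dates part of the minimum record, so partial dates should be uncommon. This stands.
- **The rule is not one-sided.** A reader might infer a systematic bias toward missing antipyretics. The reverse error of 36.2% is close to 40.8%, so that is not shown. The same rule applies in every group, and nothing suggests that arms differ.
- **Censoring does not plainly depend on these dates.** A reader might infer that titers taken after a forbidden vaccine or drug stay in the Per-Protocol Set. For day-missing starts on Days 15-28, 0.5% are imputed before the dose and 21.4% after the Day 29 sample. But SAP 6.1.3 runs exclusions through protocol deviations that are tracked, coded by visit and reviewed before database freeze, and does not say that codes come from imputed dates. The schedules of activities ask about medication and vaccination at Days 1, 8 and 29, so a vaccine first reported at Day 29 can be placed without its exact day. Protocol 5.2 bars planned non-replicating vaccines only up to 14 days after dosing, so many given on Days 15-28 would not be forbidden. The effect is possible, not established.
- **The adverse event rule does not transfer directly.** Under Protocol 8.4.1, occurrences before dosing are medical history, so anchoring events to the dose is natural. Medications and earlier COVID-19 vaccines fall on both sides. This limits the form of the fix.

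What remains is the first worked case: neither the start rule nor the stop rule looks at the dose date, and the carry-over clause cannot rescue a record whose stop was also moved to the 15th.

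**Conclusion.** The point holds as a minor gap in a derivation rule. When dosing falls after the 15th, a drug taken later in the dosing month with month-only start and stop dates, or a vaccine with a month-only date, is classed as pre-dose and leaves the descriptive concomitant medication and Day 1-28 antipyretic summaries. Year-only records have the same problem when June 30 precedes the dose.

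The percentages are shares of day-missing start dates and rest on dose dates spread evenly over the year and starts spread evenly over each window. Actual dosing calendars would shift them. The absolute effect depends on an unstated and probably low rate of partial dates. The documents do not support a claim of one-way bias, of a difference between arms, or of distorted primary titer results.

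**What to change.** Add three statements to SAP 6.2.2.1:

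1. **Start.** A medication or vaccine with a partial start that could fall on or after dosing is treated as concomitant, with the start set to the dose date if the known month or year contains it, unless the record, including the Day 1 medication and vaccination history, shows that it was given or stopped before dosing. The last condition keeps known prior drugs and earlier COVID-19 vaccines off the dose date.
2. **Stop.** Partial stop dates go to the end of the known month or year, or to last contact if earlier, as already done for adverse events.
3. **Censoring.** For a partially dated vaccine or drug, Per-Protocol Set exclusion follows the reviewed deviation record, for example the visit at which it was first reported, and not the 15th.

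The cost is a short SAP addition and a small programming change. The downside is that a few pre-dose treatments without a documented stop may be counted as concomitant. Starts in the month after dosing that are imputed past Day 28 are not changed by the start rule; the third statement covers them where censoring is concerned.

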#### **4.2.1.2. Unsolicited AEs with onset within the 28 days follow-up period (day 1-28)**

An AE is any untoward medical occurrence in a clinical study participant, temporally associated with the use of a study intervention, whether or not considered related to the study intervention. An AE can therefore be any unfavorable and unintended sign (including an abnormal laboratory finding), symptom, or disease (new or exacerbated) temporally associated with the use of a study intervention.

The verbatim reports of unsolicited AEs will be reviewed by a qualified person and the signs and symptoms will be coded according to the Medical Dictionary for Regulatory Activities (MedDRA) Dictionary for Adverse Reaction Terminology. Every verbatim term will be matched with the appropriate PT.

A study intervention causally related AE is defined as an AE for which the investigator classifies the possible relationship to study intervention as “Yes”. Investigators will not be required to assess the causality of solicited Aes if the onset is during the solicitation period.

The investigator is obligated to assess the relationship between study intervention and each occurrence of each AE/SAE/. The investigator will use clinical judgment to determine the relationship.

The percentage of participants with any unsolicited Aes within the 28-day follow up period (i.e., Day 1-Day 28) with its exact 95% confidence interval (CI) will be tabulated by group and by MedDRA PT and System Organ Class (SOC). Similar tabulation will be done for Grade 3 unsolicited Aes, for any causally related unsolicited Aes, for Grade 3 causally related unsolicited Aes, for unsolicited Aes resulting in a medically attended visit and for SAE.

A data listing for all unsolicited AEs will be provided by age group (< 65 years,  $\geq$  65 years), dose group and participant number.

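### SAP 6.2.2.1 does not bound an imputed AE start by the event's stop date or last contact, so an event shown to begin within Day 1-28 can be dated outside it

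*SAP*

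**What the plan says.** SAP section 6.2.2.1 (Dates) gives two default rules: "A missing day will be replaced by 15" and "A missing day and month will be replaced by June 30".

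Two of the exceptions for AE start dates concern missing parts of the date. When only the day is unknown: "If the event starts in the same month as the study dose administration then the imputed start date will match the study dose given". When the month is unknown too: "If the event starts in the same year as the study doses the imputed start date will match the study dose given". A third exception covers only a missing time on the day of vaccination. Every other partial start goes back to the defaults: "All other cases of incomplete AE or concomitant medication/vaccination start date will follow the standard rules above".

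The section has two safeguards, and both act on the stop date:

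- "For stop date, the maximum between the start and imputed stop date by above rule will be used instead". This can move an imputed stop but never a start.
- "Adverse events stop dates with missing day: the last day of the month or the last contact date will be used, which ever come first". Similar last-contact rules follow for stop dates with more parts missing. None is given for start dates.

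The imputed start decides whether an event enters the summary in SAP section 4.2.1.2, which reports "The percentage of participants with any unsolicited Aes within the 28-day follow up period" and is defined by onset on Day 1 to 28. This is a primary safety endpoint in both parts (Protocol Tables 5 and 6). SAP section 4.2.1.3 covers MAAEs, SAEs and AESIs with onset from Day 1 up to study end.

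**The concern.** A 28-day window usually runs into the month after dosing. For an event in that second month with no start day, the rule assigns the 15th even when the reported stop date shows that the event was already over. The reported data do not conflict: a start in April and a stop on 8 April fit together. The conflict appears only after imputation, so a check of the reported dates would not raise it.

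Two things follow for such an event. Its imputed start falls after its known stop, and it can be left out of the Day 1-28 unsolicited AE summary although its dates prove that it belongs there. The 30 June rule has the same gap when only a year after the dosing year is known. The SAP uses last contact to bound the end of an event but not its beginning, and gives no reason for the difference.

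**Working it through.** **Inputs**

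| Input | Value | Source |
|---|---|---|
| Default start, day missing | 15th of the month | SAP 6.2.2.1 |
| Default start, day and month missing | 30 June of the year | SAP 6.2.2.1 |
| Dose day | Day 1, so onset day = date - dose date + 1 | SAP 6.2.1.7 and 6.2.1.8 |
| Day 28 | dose date + 27 days | from the row above |
| Planned Day 181 | dose date + 180 days; ±7 days (Part A), ±14 days (Part B) | Protocol Tables 3 and 4 |
| Duration | stop - start + 1 | SAP 6.2.1.10 |

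Individual dosing dates are not in the documents, so those below are assumptions.

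**1. Convention check.** SAP 6.2.1.10 gives 3 to 12 March 2018 as 10 days: 12 - 3 + 1 = 10. It reproduces.

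**2. An event provably inside the window.** Dose 15 March, so Day 28 is 11 April. The AE start is April with no day, and the stop is 8 April.

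- Earliest possible onset: 1 April = Day 18. Latest: 8 April = Day 25.
- Imputed start: 15 April = Day 32, which is outside Day 1-28 and 7 days after the stop (8 - 15 + 1 = -6 days by the duration formula).

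**3. The 30 June rule.** Dose 20 December 2023. The start is known only as 2024, and the stop is 10 January 2024.

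- Possible onset: 1 January (Day 13) to 10 January (Day 22).
- Imputed start: 30 June 2024 = Day 194.

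**4. How many dosing dates are exposed.** Take a dose on day *d* of a month with *L* days. The window reaches day *k* = *d* + 27 - *L* of the next month.

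- It reaches the next month when *k* is 1 to 27: 27 dosing days per month, 27 × 12 = 324 dates in a 365-day year.
- The 15th lies beyond Day 28 when *k* is 1 to 14: 14 per month, 14 × 12 = 168 dates. In a 31-day month these are doses on the 5th to the 18th.
- Share of dosing dates: 168 / 324 = 52%.

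**5. How many onsets.** Assume true onsets are uniform over Days 1-28 and dosing is uniform over the year. A dose reaching day *k* has *k* of its 28 onset days in the next month.

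- All onset days: 365 × 28 = 10,220.
- After the dosing month: (1 + ... + 27) × 12 = 378 × 12 = 4,536, or 44.4%.
- Of these, those for which the 15th is beyond Day 28: (1 + ... + 14) × 12 = 105 × 12 = 1,260.
- If the day is missing: 1,260 / 4,536 = 27.8% of onsets after the dosing month are moved out, and 1,260 / 10,220 = 12.3% of all onsets.

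The partial-date rate is not given. If 1% to 2% of in-window AEs lacked the start day (assumption), 0.12% to 0.25% of in-window AEs would move out (0.123 × 1% to 0.123 × 2%).

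**6. 30 June against the end of follow-up.** For doses from 5 July to 31 December 2023, planned Day 181 runs from 1 January to 28 June 2024. So 30 June 2024 always lies after it, between Day 362 and Day 183. Allowing for the visit windows, 30 June is within permitted follow-up for doses from 26 December in Part A (30 June - 187 days) and from 19 December in Part B (30 June - 194 days).

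**7. With a cap at stop date and last contact.** The example in step 2 becomes 8 April, Day 25. The example in step 3 becomes 10 January 2024, Day 22. A third case is a dose on 10 October 2023, a start in April 2024 with no day, and last contact on 7 April 2024 (Day 181). It moves from 15 April (Day 189) to Day 181.

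**The case against.** The best defence is that few events will meet this rule. There is one dose, a Day 8 contact and a Day 29 visit that both record unsolicited AEs, so recall is short. SAEs and AESIs are reported within 24 hours. Partial dates in the dosing month or year already go to the dose date. The rule is the same in every arm, the study is observer-blind, and the safety analysis is descriptive. The endpoint counts participants, so a participant leaves the overall count only if the misdated event was their only one in the window. All of this stands and limits the size.

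Several stronger readings are tempting, but the documents do not support them:

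- *That 52% of next-month events are lost.* The 52% counts dosing dates. The corresponding share of onsets is 27.8%, under the uniform assumption and only among those with a missing day. Most of these need not have a stop date that proves anything.
- *That the rule always undercounts.* For the other 156 of 324 dates the 15th lies inside the window. A next-month MAAE or SAE with true onset after Day 28 could then be counted in. Mid-month imputation can err both ways; the one-sided error belongs to events whose stop date proves early onset.
- *That MAAEs, SAEs and AESIs drop out of the study-long tables.* That requires an upper onset cut-off in the program. SAP 4.2.1.3 refers to study end but specifies no such algorithm.
- *That the 30 June problem affects every 2023 dose.* For doses up to 4 July, planned Day 181 is on or before 31 December 2023, so a 2024 onset is already after it.
- *That negative durations distort a result.* The only planned duration summary is for solicited AEs. None is specified for unsolicited AEs.

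The logical gap remains: the rule can assign a start that the event's own dates rule out.

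**Conclusion.** The point holds as a gap in a stated derivation rule. Under SAP 6.2.2.1, an AE whose stop date proves onset within Day 1-28 can be given a start after that stop and be left out of a primary safety summary. This follows from the text and needs no assumption beyond the reported dates.

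Its size is probably small. The figures of 27.8% of day-missing onsets after the dosing month, and 12.3% of all day-missing onsets, rest on uniform onset and dosing dates and must be multiplied by a partial-date rate that the documents do not give. They also cover more than the provable cases, which need a known stop date or last contact on or before Day 28. Any effect on the study-long MAAE, SAE and AESI tables is conditional on an onset cut-off that is not specified. The correction is worth making because it costs almost nothing and removes impossible dates from a primary endpoint.

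**What to change.** Add one sentence to SAP 6.2.2.1: an imputed AE start date is the earliest of the standard-rule date, the AE stop date (if known) and the last contact date, and is not before the dose date when the known parts of the date show onset after dosing. The existing exceptions for the dosing month and dosing year stay as they are.

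The cost is that sentence and one programming rule. Design, data collection and the other date rules are unaffected. The cap corrects only events that a stop date or last contact bounds; other day-missing starts stay on the 15th. Replacing the 15th by the first of the month would be a separate choice, with a bias in the opposite direction, and is not needed to close the gap.
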